3.5.1 Treatment Regimen

We have chosen an intra-patient dose escalation strategy because there is no previous data from human studies to demonstrate the safety of simvastatin in combination with sirolimus or everolimus, in patients with LAM-S and LAM-TS. Dose escalation strategy will be performed only for patients who tolerate 20 mg daily simvastatin. If patients do not tolerate the 20 mg simvastatin dose, the dose will be down-titrated to 10 mg daily. If 20 mg daily is well tolerated, at visit 4 the dose will be increased to 40 mg daily for months 3 and 4. If 40 mg daily is not well tolerated, the dose will be reduced back to 20 mg daily.

Intermediate dose reductions to 15 or 30 mg/day may be undertaken if the side effect(s) is reasonably mild and tolerable.

[figure not shown]
Patients will remain on their current dose of sirolimus or everolimus without interruption, as clinically indicated.

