4.1 Study and Timeline Overview

The study will enroll up to 10 evaluable patients over 3-6 months. All study patients will be assigned to a starting dosage of 20 mg of simvastatin daily for a period of two months. If patient tolerability to the 20 mg simvastatin dosage decreases, the dose will be down-titrated to 10 mg daily. Intra-patient dose escalation strategy will be performed only for patients who tolerate simvastatin 20 mg daily and the daily dosage of simvastatin will be escalated to 40 mg daily during months 3 and 4. . Patients who are escalated to 40 mg daily who do not tolerate that dose, will be reduced back down to the previously tolerated 20 mg daily.

The patient will be given a copy of the informed consent form. Patients will be given ample time to read and discuss the consent form with the study staff. The study staff will then answer any outstanding questions asked by the patient. The patient will be offered the option of signing the consent form. Those who agree to participate will undergo the remainder of screening at visit 1.

Prior to starting study drug, pulmonary function tests and chest X-ray will be obtained. The spirometry values obtained that contain the best values for FEV1, FVC and DLCO will constitute the baseline values. Patients will be followed with serial VEGF-D levels collected at each visit over a four month period.

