5.1 Definition of Dose Limiting Toxicity (DLT)

DLTs will be defined by toxicity occurring during the first 5 weeks of this study. A DLT will be any non-pulmonary AE of Grade 3 or higher that is at least possibly treatment-related with the exception of nausea and vomiting which have not been treated with optimal anti-emetic therapy. Any DLT that causes a patient to miss > 28 consecutive days of simvastatin will result in the patient being taken off treatment.

A DLT is defined as a toxicity considered at least possibly related to simvastatin. In this regard, it is important to consider the possibility that co-administration of simvastatin may increase the toxicity of sirolimus or everolimus. Conversely, sirolimus or everolimus might influence the toxicity profile of simvastatin. Thus, it may be difficult to confidently attribute certain observed toxicities solely to either simvastatin and sirolimus, or simvastatin and everolimus. With this potential complication in mind, an attempt will be made to define dose-limiting toxicities (DLTs), which apply specifically to simvastatin. In this study, DLTs will include any possibly, probably, or definitely simvastatin-related Grade 3 or 4 toxicity. Known toxicities specific to sirolimus and everolimus such as mucositis will not be considered dose limiting unless the treating physician considers the toxicity to be exacerbated by simvastatin. Toxicities that will be attributable to simvastatin include but are not limited to abdominal pain, nausea, diarrhea, headache, and infectious complications.

The target DLT rate is $\leq 33\%$. The maximum tolerated dose (MTD) will be defined as a) the dose producing DLT in 2 out of 6 patients, or b) the dose level below the dose which produced DLT in ≥ 2 out of 3 patients, or in ≥ 3 out of 6 patients. Patients will be evaluable for a DLT if they have finished 5 weeks of combined therapies. Patients who are removed from study due to clinical progression prior to the 5 week period will be replaced. Patients will be evaluable for response if they have completed 90% of their expected dose of simvastatin for the 8 weeks. Patients will be evaluated for toxicity if they received at least one dose of simvastatin.

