7.2 Criteria for Terminating the Study

Up to ten patients will be enrolled in this study. The maximum duration of patient participation is up to 164 days, including a follow-up phone contact one month after the last study visit. In the event of any death, or Grade III SAE attributable to the study agent, enrollment and treatment will be suspended, pending Data Safety Monitoring Board (DSMB) review.

8. Study Variables and Measuring Methods

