9.2 Safety Monitoring and Adverse Event Reporting

Patients will be evaluated for safety if they have received at least one dose of simvastatin. The frequency, severity and duration of all adverse events, regardless of cause, will be recorded on the case report forms. The frequency and severity of adverse events will be calculated by patient. The most severe grade of adverse event experienced by patient will be counted once. The duration of adverse events will be calculated by the number of days each event persisted. Adverse events will be tabulated by body system and by severity using the NCI Common Terminology Criteria for Adverse Events v4.0, which can be obtained from the CTEP Website: <http://ctep.cancer.gov/reporting/ctc.html>. Tables will be generated for all adverse events including those that are judged to be possibly, probably or definitely related to the simvastatin.

All adverse events will be reviewed by a DSMB created for this study and composed of pulmonologists [name]., [name], M.D., and [name]. Any serious AE (generally grade 3 or 4 toxicity or defined by lead pulmonologist) will result in patient discontinuation of simvastatin until the DSMB

reviews the case and make a recommendation made regarding re-institution of the study drug.

As this is a safety study with a small number of patients, data will be compiled in descriptive tables of results. A study participation summary will be written for each patient and for trends in the data. Special attention will be given to adverse reactions to the simvastatin and any changes in the pulmonary function testing or the laboratory values outside of normal ranges.

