9.3.1 Serious Adverse Events

A serious adverse event is any adverse drug experience occurring at any dose that:

- Results in death;
- Is life-threatening;
- Results in inpatient hospitalization or prolongation of existing hospitalization;
- Results in congenital anomaly or birth defect;
- Results in a persistent or significant disability/incapacity; or
- Important medical events that may not result in death, be life-threatening, or require hospitalization may be considered serious adverse drug experiences when, based upon appropriate medical judgment, they may jeopardize the patient and may require medical or surgical intervention to prevent one of the outcomes listed in this definition. Examples of such medical events include allergic bronchospasm requiring intensive treatment in an emergency room or at home, blood dyscrasias or convulsions that do not result in inpatient hospitalization, or the development of drug dependency or drug abuse.

A life-threatening adverse event is any adverse drug experience that places the patient at immediate risk of death from the reaction as it occurred; ie, it does not include a reaction that, had it occurred in a more severe form, might have caused death.

Initial hospitalization is defined as any inpatient admission (even if less than 24 hours). For chronic or long-term inpatients, inpatient admission also includes transfer within the hospital to an acute/intensive care inpatient unit (eg, from the psychiatric wing to a medical floor, from a medical floor to the coronary care unit, from the neurological floor to the tuberculosis unit).

Inpatient admission in the absence of a precipitating, treatment-emergent, clinical adverse event may meet criteria for “seriousness” but is not an adverse experience and thus is not subject to immediate reporting. For example:

- Admission for treatment of a pre-existing condition not associated with the development of a new adverse event or with a worsening of the pre-existing condition (eg, for work-up of persistent pretreatment lab abnormality)
- Social admission (eg, patient has no place to sleep)
- Administrative admission (eg, for yearly physical exam)
- Protocol-specified admission during the clinical study (eg, for a procedure required by the study protocol)
- Optional admission not associated with a precipitating clinical adverse event (eg, for elective cosmetic surgery)
- Hospitalization for what is clearly progressive disease

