9.3.2 Abnormal Laboratory Test Results

Laboratory results will be assessed for adverse events as described in CTCAE v4.0 using normal ranges specified for the institution's laboratory.

The results of all laboratory tests required by the protocol will be recorded in the patient's case report form. All clinically important abnormal laboratory tests occurring during the study will be repeated at appropriate intervals until they return either to baseline or a level deemed acceptable by the investigator or until a diagnosis that explains them is made. The criteria for determining whether an abnormal laboratory test result should be reported as an adverse event are as follows:

- Test result is associated with accompanying symptoms, and/or
- Test result leads to a change in study dosing or discontinuation from the study, significant additional concomitant drug treatment or other therapy, and/or
- Test result leads to any of the outcomes included in the definition of a serious adverse event, and/or
- Test result is considered to be an adverse event by the investigator or sponsor.

Merely repeating an abnormal test, in the absence of any of the above conditions, does not meet Condition 2 above for reporting as an adverse event.

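### The DLT counts by which Section 5.1 puts a dose above the MTD trigger no hold on enrolment or on the step to 40 mg, and Section 7.2 fills the gap only on one of two readings of serious

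*Combined protocol and SAP*

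**What the plan says.** **DLTs and MTD (Section 5.1).** "DLTs will be defined by toxicity occurring during the first 5 weeks of this study", a period in which the planned dose is 20 mg. A DLT is, in essence, a non-pulmonary event of Grade 3 or higher that is at least possibly related to treatment. The target DLT rate is at most 33%. The MTD is either the dose giving DLTs in 2 of 6 patients, or "the dose level below the dose which produced DLT in" at least 2 of 3, or at least 3 of 6, patients. The only action the section attaches to a DLT is individual: a patient who misses more than 28 consecutive days because of one comes off treatment.

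**Step to 40 mg.** Section 3.5.1: "If 20 mg daily is well tolerated, at visit 4 the dose will be increased to 40 mg daily". Section 4.1: "Intra-patient dose escalation strategy will be performed only for patients who tolerate simvastatin 20 mg daily". Section 4.3.4 (Visit 4) dispenses 40 mg unless contraindicated. Each condition concerns that patient alone.

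**Study-level hold (Section 7.2).** "In the event of any death, or Grade III SAE attributable to the study agent, enrollment and treatment will be suspended", pending DSMB review. The section mentions no DLT, count or MTD.

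**Meaning of serious.** Section 9.2 goes by grade: "Any serious AE (generally grade 3 or 4 toxicity or defined by lead pulmonologist) will result in patient discontinuation of simvastatin until the DSMB" has reviewed the case. Section 9.3.1 goes by outcome: "A serious adverse event is any adverse drug experience occurring at any dose that" leads to death, threat to life, hospitalisation and the other listed outcomes, including medically important events by judgment.

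**Other controls.** Section 5.2.3 holds and then reduces the affected patient's dose for a related event of Grade 3 or higher. Section 9.2 sends all adverse events to the DSMB. Section 9.4.1 requires an IRB report if a side effect proves more frequent than expected. Sections 11.1 and 11.2 give confidence intervals and descriptive tables, with no decision rule.

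**The concern.** The plan states the counts at which it would call a dose too toxic, and then does nothing when they are reached. If 20 mg met them through events that do not trigger Section 7.2, new patients would still start on 20 mg, and those who individually tolerated it would still be doubled to 40 mg.

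Safety is the primary objective. Section 3.5.1 says there are no prior human data showing the safety of the combination in these patients, and Section 1.4.1 describes a shared metabolic route and a reported case of rhabdomyolysis with renal failure on simvastatin plus rapamycin.

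**Working it through.** **1. The plan's own DLT figures.** Table 5 gives the chance of seeing no DLT in 9 patients. With (1-p)^9 at p = 11%, 22%, 33%, 44% and 56% I get 35.0%, 10.7%, 2.7%, 0.5% and 0.06%, which agrees with that row. The plan gives no corresponding figure for the 5.1 counts.

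**2. What a related, non-serious Grade 3 event at 20 mg sets in motion.**

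| Provision | 9.2 meaning (by grade) | 9.3.1 meaning (by outcome) |
|---|---|---|
| 7.2 study hold | Fires at the first attributable event | Does not fire |
| 5.2.3 hold and reduction | That patient | That patient |
| DSMB review of the event (9.2) | Yes | Yes |
| 5.1 count reached | No stated action | No stated action |
| Other patients' step to 40 mg | Suspended by 7.2 until released | Continues |

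Such events can exist on the outcome-based meaning. For laboratory results, Section 9.3.2 lists a change in study dosing as one reason for reporting an adverse event, and "Test result leads to any of the outcomes included in the definition of a serious adverse event" as a separate one.

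**3. How often the counts are reached.** Inputs: p is the true DLT rate and s the share of DLTs that are serious under 9.3.1. Both are assumptions, since the documents give neither for the combination. Patients are taken as independent and their outcomes as known in order of first dose. Put q = p(1-s) for a non-serious DLT and n = 1-p for none. The chance of reaching at least 2 of the first 3 or at least 3 of the first 6, with no serious DLT up to and including the patient who completes the count, is

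A + 3qn²·A + n³q³, where A = q²(1+2n).

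Example, p = 0.33 and s = 0.5: q = 0.165, n = 0.67, A = 0.0272 × 2.34 = 0.0637. The sum is 0.0637 + 0.2222 × 0.0637 + 0.3008 × 0.0045 = 0.079.

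| Share serious | p = 10% | 20% | 33% | 50% |
|---|---|---|---|---|
| 0 (counts reached at all) | 3.6% | 14.8% | 37.9% | 70.3% |
| 25% | 1.9% | 7.7% | 19.6% | 36.7% |
| 50% | 0.8% | 3.2% | 7.9% | 15.0% |
| 100%, or 9.2 meaning | 0 | 0 | 0 | 0 |

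If instead no serious DLT is allowed anywhere in the block of 3 or 6, the two middle rows at 33% become 18.9% and 7.4%. At p = 1.4%, the simvastatin discontinuation rate in Section 1.4.1, the top row is 0.06%.

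**4. Whom a hold could still protect.** Assume 10 patients accrue evenly, on days 0, 10, ..., 90 (3 months) or 0, 20, ..., 180 (6 months).

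| When patient 3's 5-week window closes | 3 months | 6 months |
|---|---|---|
| Study day | 20+35 = 55 | 40+35 = 75 |
| Enrolled | 6 | 4 |
| Still to enrol | 4 | 6 |
| Enrolled and past own Day 60 | 0 | 1 |
| Enrolled and awaiting 40 mg | 6 | 3 |
| Of these, without a DLT (at most) | 6-2 = 4 | 3-1 = 2 |

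In the last row at least 2 of patients 1 to 3 have had a DLT. Under 6-month accrual one of those may be patient 1, who is already past Day 60, so at least one DLT falls among the three still waiting.

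When patient 6's window closes (50+35 = day 85, or 100+35 = day 135), 9 or 7 are enrolled, 1 or 3 are still to enrol, and 3 or 4 are past their own Day 60.

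**The case against.** The strongest reply is that Section 7.2 is already stricter than the counts. It suspends enrolment and treatment at one event. It attaches a grade to SAE and routes the case to the DSMB, just as Section 9.2 does when it glosses serious as generally Grade 3 or 4. On that reading nearly every DLT pauses the study. This stands as a reading, but it is not the only one: Section 9.3.1 is the formal definition, and Section 5.2.3 handles related Grade 3 events patient by patient without mentioning a study pause.

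Second, the DSMB reviews every adverse event, so in a single-site study of at most 10 patients it would already have seen the two or three cases. That also stands. What the plan lacks is a hold while they are considered together.

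Third, every rate above is assumed, and at the one rate taken from the document, for simvastatin alone, the chance is negligible. The point therefore matters only if the combination is clearly worse than simvastatin alone.

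Fourth, the counts fit this design imperfectly. The DLT window closes before Day 60, so they cannot detect toxicity first seen at 40 mg, and they say nothing after patient 6. Both limits stand.

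A reader might infer that the trial has no pooled stopping rule, or that the DSMB would be unaware of accumulating DLTs. Sections 7.2 and 9.2 contradict both. A reader might also suppose that a hold at patient 3 would spare the 10 or 9 patients who have not yet reached Day 60. That number includes patients not yet enrolled and the DLT patients themselves, whose drug Section 5.2.3 already holds and reduces.

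**Conclusion.** The point holds in a limited form. No section acts on the 5.1 counts, and escalation is decided patient by patient.

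- **Outcome-based meaning (9.3.1):** related non-serious Grade 3 events at 20 mg could reach the counts while enrolment and steps to 40 mg go on. At an assumed DLT rate of 33% the chance is about 8-20% if a quarter to a half of DLTs are serious, and 38% if none are.
- **Grade-based meaning (9.2):** the gap is nil until the DSMB lifts a 7.2 pause.

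On either meaning the patient-level holds and DSMB review remain, so the added protection is modest: 4 or 6 patients still to enrol and at most about 4 or 2 enrolled patients awaiting 40 mg without a DLT. These figures rest on the assumed rates, independence and even accrual. This is a cheap safety improvement that should be made. It is not an error in a stated figure, and the documents do not show that patients would be escalated without oversight.

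**What to change.** Keep the existing 7.2 trigger and add two things to that section.

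- When DLTs, serious or not, reach at least 2 of the first 3 or at least 3 of the first 6 patients in order of first dose, enrolment and pending steps to 40 mg are held until the DSMB has reviewed the pooled data. A DLT counts when it occurs, and early progressors are replaced as in Section 5.1. The DSMB decides what follows, including for patients already on 20 or 40 mg.
- State which meaning of serious applies in 7.2.

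This uses the existing board and data. The cost is pauses at acceptable doses. At a true DLT rate of 33%, which Section 5.1 accepts, the hold fires with probability about 38%, or about 8-20% with no prior 7.2 pause if a quarter to a half of DLTs are serious. Of the 38%, 3p²(1-p)^4 = 3 × 0.1089 × 0.2015 = 6.6 percentage points are runs that fire at 2 of 3 yet would finish at exactly 2 of 6, which Section 5.1 allows. That is why the action should be a review and not a stop. The rule covers only toxicity in the first 5 weeks, at 20 mg.

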Since simvastatin and rapamycin are metabolized by the same enzyme, using them together can potentially increase the blood levels or add to the side effects of either medication. Because they bind to the same protein, the drugs compete for binding sites and may have antagonistic effects when used together. Competition can potentially result in elevated concentration of sirolimus, increasing the risk of myopathy or rhabdomyolysis (42). This may have a dangerous side effect on the muscles; so, patients should be monitored for muscle pain or weakness. There have not been many clinical reports on the interactions between simvastatin and rapamycin. However, one report explains the severe interaction between simvastatin and rapamycin which resulted in rhabdomyolysis in a liver transplant patient. A 56 year old man underwent liver transplantation and was simultaneously administered rapamycin and simvastatin. Thereafter, he experienced severe muscle pain and was unable to ambulate. He suffered from rhabdomyolysis and acute renal failure probably due to secondary drug interaction between simvastatin and rapamycin (43). Due to the pharmacokinetic interaction between these two agents, they

should be administered hours apart since co-administration can increase the risk of side effects. Dosage modification of sirolimus may also ameliorate the hyperlipidemic effects (42).

The study will use generic simvastatin 20 mg and 40 mg for daily oral administration. Simvastatin 40 mg daily is the recommended dosage for patients at high risk for cardiac events, due to existing coronary heart disease, diabetes, peripheral vascular disease, history of stroke or other cerebrovascular disease. Simvastatin has been extensively studied at the recommended dose of 40 mg per day (5). Simvastatin is metabolized by cytochrome P450 isoform 3A4 (CYP3A4). The primary indications include secondary prevention for coronary artery disease and for treatment of hypercholesterolemia. Drug interactions include a slight potentiation of warfarin anticoagulant effect and mild increase in serum digoxin concentration, neither of which are clinically significant.

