5.2.4 Sirolimus or Everolimus Dose Reduction

Known sirolimus and everolimus toxicities will not be attributed to simvastatin but will only be attributed to sirolimus or everolimus and will result in the following sirolimus or everolimus dose modifications. Pulmonary toxicity of unexpected severity may be attributed to simvastatin (in addition to sirolimus or everolimus) at investigator discretion. Non-pulmonary toxicities of possible, probable or definite and definite and having an attribution to sirolimus or everolimus will result in the following sirolimus or everolimus dose modifications. Blood counts will be evaluated weekly. Within -3 days prior to sirolimus or everolimus dosing, the patient must have an ANC $> 1.0 \times 10^9/L$ and platelet count $> 75 \times 10^9/L$. All non-pulmonary toxicity grade 3 or 4 (except for mucositis, diarrhea, nausea, and acneiform rash) must have resolved to CTCAE grade \leq 2. If toxicity persists, treatment should be delayed by one week for up to 3 consecutive

weeks. If after 3 weeks of delay, all toxicity has still not resolved, then any further treatment with sirolimus or everolimus should be stopped. Simvastatin may be continued after sirolimus or everolimus has been stopped.

If any non-pulmonary toxicity observed Grade ≥ 3 (except for mucositis, diarrhea, nausea, acneiform rash, and swelling of extremities) and/or if platelets $< 75 \times 10^9/L$ and/or ANC $< 1 \times 10^9/L$, causing delay of two weeks of sirolimus then the dose should be reduced by one dose level (Table 5). For patients requiring more than 2 dosage reductions, sirolimus or everolimus will be stopped. If any non-pulmonary toxicity observed was CTCAE **Grade 4** (except for mucositis, diarrhea, nausea, acneiform rash, and swelling of extremities) then sirolimus or everolimus should be stopped.

Table 4: Sirolimus or Everolimus dose level modification guidelines

Dose reduction	Dose and schedule
Starting dose	10 mg daily
1	5 mg daily
2	5 mg every other day

6. Duration of Participation

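### Sections 5.1 and 5.2.4 conflict on whether a known sirolimus/everolimus toxicity worsened by simvastatin can be attributed to simvastatin, so the 7.2 pause is unclear for such events

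*Combined protocol and SAP*

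**What the plan says.** Section 7.2 sets the study-wide pause: "In the event of any death, or Grade III SAE attributable to the study agent, enrollment and treatment will be suspended", pending DSMB review. The agent is simvastatin; the treatment table in the protocol summary lists no other.

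The protocol expects an interaction. Section 1.4.1 says "Competition can potentially result in elevated concentration of sirolimus", and section 5.1 says "it is important to consider the possibility that co-administration of simvastatin may increase the toxicity of sirolimus or everolimus".

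Two sections then deal with known mTOR-inhibitor toxicities:

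- Section 5.1, on DLTs, says that they "will not be considered dose limiting unless the treating physician considers the toxicity to be exacerbated by simvastatin". It ties DLTs to the first 5 weeks.
- Section 5.2.4, on sirolimus/everolimus dose reduction, says "Known sirolimus and everolimus toxicities will not be attributed to simvastatin but will only be attributed to sirolimus or everolimus". It allows one exception: "Pulmonary toxicity of unexpected severity may be attributed to simvastatin (in addition to sirolimus or everolimus) at investigator discretion".

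Sections 9.2 and 11.2 tabulate all adverse events, including those judged possibly, probably or definitely related to simvastatin. Section 9.3 requires the investigator to give a causality opinion.

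**The concern.** The trial asks whether simvastatin can safely be added to an mTOR inhibitor. A sirolimus or everolimus toxicity made worse by simvastatin is therefore one of the harms it exists to detect. Section 5.1 leaves room to recognise that harm. Section 5.2.4, taken at its word, does not, because it makes attribution to the mTOR inhibitor exclusive.

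Two investigators could each follow the protocol and classify the same event differently. On one classification the whole study pauses. On the other, only the affected patient stops simvastatin, the remaining patients go on enrolling and dosing, and the event is missing from the simvastatin-related rows of the safety tables.

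**Working it through.** No figure in the plan is at issue, so the check compares the sections and then traces one event through them.

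**Step 1. What each section decides.**

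| Section | What it decides | mTOR-inhibitor toxicity worsened by simvastatin |
|---|---|---|
| 5.1 | whether an event is a DLT | counts if the treating physician considers it exacerbated |
| 5.2.4 | sirolimus/everolimus dose changes, in attribution language | not attributed to simvastatin, except unexpectedly severe pulmonary toxicity |
| 7.2 | study-wide pause | any death; otherwise needs attribution to the study agent |
| 9.2, 11.2 | adverse event tables | in the all-event table regardless; in the related rows only if judged related |
| 9.2 | hold for one patient | any serious event, no attribution needed |
| 9.3 | causality opinion | required; not said to prevail over 5.2.4 |

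**Step 2. How much of treatment the 5.1 exception covers.** The DLT window is 5 × 7 = 35 days. Planned treatment is 120 days, so 120 − 35 = 85 days (85/120 = 71%) fall outside it. The step to 40 mg comes at visit 4, nominally day 60. Even with both visit intervals at their shortest (30 − 7 = 23 days each), visit 4 falls on day 23 + 23 = 46, still after day 35. The whole 40 mg period therefore lies outside the exception.

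**Step 3. One event traced through.** Take a non-fatal, non-pulmonary Grade 3 SAE on day 75. It is of a type known for sirolimus, and the investigator thinks simvastatin possibly made it worse.

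- Under 5.1 it is not a DLT, because it falls after week 5.
- If the 9.3 opinion governs, it is possibly related to simvastatin. It pauses the study under 7.2 and enters the related rows.
- If 5.2.4 governs, it is not attributed to simvastatin. No pause is required and it stays out of the related rows.
- Either way, simvastatin is held in that patient, the DSMB reviews the case and the IRB is told.

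**Step 4. Size.** With the ten patients that 7.2 allows, at most 10 − 1 = 9 others could still be dosing when the event occurs. The documents give no rate *p* for such events. For scale only, *p* is assumed below. The chance that these events cause at least one pause is 1 − (1 − *p*(1 − *s*))^10, where *s* is the share left unattributed under 5.2.4 and patients are independent.

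| Assumed *p* | *s* = 0 | *s* = 0.5 | *s* = 1 |
|---|---|---|---|
| 5% | 40% | 22% | 0% |
| 10% | 65% | 40% | 0% |
| 20% | 89% | 65% | 0% |
| 33% | 98% | 84% | 0% |

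These figures show how much the choice of reading matters at each assumed rate. They do not forecast that such an event will occur.

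**The case against.** The best answer is that 5.2.4 is a dosing rule. Its heading and parent section concern dose changes, and its sentence runs on to dosing: such toxicities "will only be attributed to sirolimus or everolimus and will result in the following sirolimus or everolimus dose modifications". Neither 7.2 nor the table sections refer to it. Causality has its own home in 9.3, with no exclusion for mTOR-inhibitor toxicities, and the tables use events as judged. This is a plausible account of the intent, so it would be wrong to say that nothing limits 5.2.4. It does not settle the matter. The next sentence of 5.2.4 makes an exception about attribution to simvastatin, which a rule purely about sirolimus/everolimus dosing would not need, and no section says which prevails.

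Three further objections stand and narrow the point:

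- The word attributable in 7.2 need not mean something stricter than possibly, probably or definitely related. Section 5.2.3 speaks of attribution in just those terms. The gap comes from 5.2.4, not from that word.
- The plan does not list the known mTOR-inhibitor toxicities. Mucositis is the one example named in 5.1, and Tables 2A and 2B treat it as overlapping, with simvastatin reduced second. Cytopenia could be inferred from the blood-count conditions in 5.2.4 ("Within -3 days prior to sirolimus or everolimus dosing, the patient must have an ANC" above a threshold, with a platelet minimum), but it is not named as a known toxicity. The simvastatin lists in 5.1 and 5.2.3 are not closed, and a laboratory Grade 3 cytopenia need not meet the seriousness criteria in 9.3.1.
- Other safeguards do not depend on attribution to simvastatin. They are the pause for any death, the 9.2 hold, DSMB review of all adverse events, and IRB reporting of SAEs under 9.3.1.

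**Conclusion.** The conflict is real and should be resolved, but its reach is limited. It affects serious, non-fatal, non-pulmonary toxicities of a kind known for sirolimus or everolimus that simvastatin may have worsened. For those, two things are unclear: whether the whole study pauses, and whether the event is tabulated as simvastatin-related. The question is sharpest after week 5 and throughout the 40 mg period, where 5.1 offers no exception. For one such event, the literal reading of 5.2.4 changes the pause from required to not required, with at most nine other patients still dosing during DSMB review.

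A reader might infer two stronger conclusions that the documents do not support. One is that such events escape safety review. They do not, because the patient-level hold, DSMB review and IRB reporting remain. The other is that a misattributed event would distort a planned confidence interval. The plan gives intervals only for DLTs (Table 5 in 11.1), where the 5.1 exception applies, and the related-event tables are descriptive.

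The conclusion assumes that an investigator might follow the words of 5.2.4. If every investigator reads that section as dosing only and lets 9.3 govern, nothing is lost.

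**What to change.** 1. Add to 5.2.4: *This rule applies to sirolimus/everolimus dose modification only. For section 7.2 and adverse event tabulation, such a toxicity is also attributed to simvastatin when the investigator considers it at least possibly caused or exacerbated by simvastatin.*
2. Word the 7.2 trigger as: *any death, or any Grade 3 or higher SAE at least possibly related to simvastatin, including through its interaction with sirolimus/everolimus.* Stating Grade 3 or higher removes doubt about Grade 4, which 7.2 does not name.

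Events judged related only to background sirolimus or everolimus would still not pause the study. The blood levels already scheduled in Table 1 (screening and days 30, 60, 90 and 120) can inform the judgment, so no new test or committee is needed. The cost is a wording amendment, plus an occasional extra suspension and DSMB review when the investigator cannot exclude an interaction.
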